6.2 RESPONSE CRITERIA

6.2.1 Response assessments will be performed on Day 1 (+/- 3 days) of cycles 2, 4 and 7; and on Day 1 (+/-3 days) of every third cycle starting at cycle 10 at scheduled clinic visits, at the time of documented CR, and at disease progression Disease Parameters

- Patients who have a measurable serum or urine M-protein. A "measurable" serum M-protein is ≥ 1 g/dL and a "measurable" urine M-spike is ≥ 200 mg/24 hours. If patient does not have a "measurable" serum or urine M-protein, but has either a serum kappa or lambda FREE light chain of 10 mg/dL along with an abnormal kappa to lambda free light chain ratio, patient is considered to have "measurable" disease.
- The serum free light chain (FLC) assay is of particular use in monitoring response to therapy in patients who have oligo-secretory disease. When using this assay, it is important to note that the FLC levels vary considerably with changes in renal function and do not solely represent monoclonal elevations. Thus both the level of the involved and the uninvolved FLC isotype (i.e., the involved/uninvolved ratio or involved-uninvolved difference) should be considered in assessing response. The serum FLC assay should be used in assessing response only if the baseline serum and/or urine M proteins are not "measurable" by traditional criteria (serum M protein ≥ 1 gm/dL and/or urine M protein ≥ 200 mg/24), and the baseline level of the involved FLC is 10mg/dL and clonal (abnormal ratio). Patients included on the study on the basis of FLC alone (i.e., no measurable serum/urine) should be the only ones who are evaluated using FLC response criteria. The others should follow usual criteria and ignore FLC results.
- In order to be classified as a hematologic response, confirmation of serum monoclonal protein, serum immunoglobulin free light chain (when primary determinant of response) and urine monoclonal protein (when primary determinant of response) results must be made by verification on two consecutive determinations.
- Caution must be exercised to avoid rating progression or relapse on the basis of variation of radiological technique alone. Compression fracture does not exclude continued response and may not indicate progression. When progression is based on skeletal disease alone, it should be discussed with the PI before removing the patient from the study.

6.2.2 Response Criteria from International Myeloma Workshop Consensus Panel Criteria⁴⁷:

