3.2 DRUG ADMINISTRATION

- Lenalidomide 10 mg once daily, given by mouth on days 1-21, of repeated 28-day cycles, to continue until disease progression, unacceptable toxicity or completion of two years of lenalidomide therapy and the 30 day safety follow-up visit.
- Lenalidomide will be prescribed monthly by Clinical Center physicians. Upon completion of phone counseling per the REMS® program, the NIH Clinical Center physician will prescribe a 28 day supply of lenalidomide to be sent to the patient by express delivery beginning with Cycle 4.

Abbreviated Title: Revlimid maintenance for MM

Version Date: 01/06/2017

- Females of childbearing potential (FCBP) patients will be required to have pregnancy testing as outlined in Appendix B: Risks of Fetal Exposure, Pregnancy Testing Guidelines and Acceptable Birth Control Methods: Risks of Fetal Exposure, Pregnancy Testing Guidelines and Acceptable Birth Control Methods; and may have the pregnancy test performed by local treating physician. In these cases, the local physician will submit the results to NIH Clinical Center for review. Upon receipt of negative pregnancy test result and completion of phone counseling per the REMS® program, NIH Clinical physician will prescribe a 28 day supply of lenalidomide to be sent to the patient by express delivery.
- Lenalidomide capsules should be swallowed whole, and should not be broken, chewed or opened.
- If vomiting occurs within 15 minutes and the whole capsule is present in the emesis then the dose can be repeated.
- If a dose of lenalidomide is missed, it should be taken as soon as possible on the same day. If it is missed for the entire day, it should not be made up.
- Patients who take more than the prescribed dose of lenalidomide should be instructed to seek emergency medical care if needed and contact study staff immediately.

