- 3.3.5.2 Random urine sample for protein electrophoresis (UPEP) and immunofixation to assess for monoclonal protein in the urine (Bence-Jones proteinuria) will be performed at baseline, on Day 1 (within 3 days prior) of cycles 2, 4 and 7 and on Day 1 (within 3 days prior) of every third cycle starting at cycle 10 at scheduled clinic visits, at the time of documented CR, and at disease progression (see study calendar).
- 3.3.5.3 Myeloma tests including serum protein electrophoresis, serum immunofixation, serum free light chains, quantitative immunoglobulins, beta-2 microglobulin will be performed at baseline, on Day 1 (within 3 days prior) of cycles 2, 4 and 7 and on Day 1 (within 3 days prior) of every third cycle starting at cycle 10 at scheduled clinic visits, at the time of documented CR, and at disease progression (see study calendar).
- 3.3.5.4 Patients will have clinic visits with H&P or standard progress notes assessing for toxicity/side effects on Day 1 (within 3 days prior), and 15 (within 3 days prior) of cycle 1 and Day 1 (within 3 days prior) of cycles 2, 4 and 7 and on Day 1 (within 3 days prior) of every third cycle starting at cycle 10 at scheduled clinic visits (see study calendar).
- 3.3.5.5 Skeletal survey to assess disease status will be performed at baseline. The skeletal survey at the time of documented CR or disease progression is optional.
- 3.3.5.6 Evaluation of bone marrow for disease status will be performed at baseline, and then at the time of documented CR or disease progression. Additional bone marrow samples to evaluate disease status, treatment effect, or biomarker studies will be obtained at the discretion of PI, if patients are willing.
- 3.3.5.7 Additional laboratory studies and clinic visits may be performed as clinically indicated.
- 3.3.5.8 Patients removed from protocol therapy for unacceptable adverse events will be followed until resolution or stabilization of the adverse event. Further follow-up can be assessed either by phone consultation or clinic appointment at the discretion of the PI.

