- l. Patients removed from protocol therapy for unacceptable toxicities will be followed until resolution or stabilization of the adverse event. Further follow-up for patients taken off protocol therapy can be assessed either by phone consultation or clinic appointment at the discretion of the PI.
- m. Day 1 may be delayed for up to one week for Cycle 2 and beyond.

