3.5 CRITERIA FOR REMOVAL FROM PROTOCOL THERAPY AND OFF STUDY CRITERIA

3.5.1 Criteria for removal from protocol therapy

- 3.5.1.1 Patients with medically concerning grade 3 or 4 adverse events related to study drug may be taken off therapy at the discretion of the principal investigator.
- 3.5.1.2 Toxicity has not resolved after 8 weeks of withholding treatment
- 3.5.1.3 Grade 4 non-blistering rash, or blistering rash of any grade
- 3.5.1.4 Grade 4 neuropathy
- 3.5.1.5 Grade 4 hypersensitivity reaction
- 3.5.1.6 Progression of disease
- 3.5.1.7 Patient chooses to go off therapy
- 3.5.1.8 The principal investigator may remove patient from protocol therapy if deemed necessary due to medical conditions, compliance, etc.
- 3.5.1.9 Diagnosis of new malignancy
- 3.5.1.10 Patient becomes pregnant.

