8 STATISTICAL CONSIDERATIONS

8.1 STUDY DESIGN/PRIMARY ENDPOINTS

This is a single arm, single stage, phase II trial to evaluate maintenance therapy with the immunomodulatory agent lenalidomide in treated MM patients who have stable or responsive disease. After screening, eligibility determination, and enrollment; subjects will receive lenalidomide 10 mg by mouth daily on days 1-21 of a 28-day cycle. Subjects may continue lenalidomide until disease progression, diagnosis of new malignancy, unacceptable toxicity, investigator discretion, or voluntary withdrawal. When necessary, lenalidomide will be held and restarted in accordance with accepted clinical dose modification strategies.

The primary objective of this study is a longitudinal assessment of T cell (CD4, CD8), NKT and NK cell populations during the course of lenalidomide maintenance therapy in patients with MM. Using flow cytometry on peripheral blood obtained at baselines and after 3 cycles of therapy, we will determine the primary measures at both time points. Comparisons at other time points will be considered exploratory..

With 28 patients enrolled, we will have 80% power to detect an effect equal to 0.67 SD of the difference in counts (0.67 SD effect size) of T cells (CD4, CD8), NKT and NK cells with a two-tailed paired t-test and a significance level of 0.013 for each test. Thus, using a strict Bonferroni adjustment, we would have an overall significance level of 0.05 for the four tests. In practice, a less overly conservative Hochberg adjustment may be used instead of a Bonferroni adjustment. In addition, if the difference in the numbers of any type of cells is not normally distributed ($p < 0.05$ by a Shapiro- Wilks test), then a Wilcoxon signed rank test will be performed instead.

Results will be presented in a descriptive format.

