8.3 STATISTICAL ANALYSIS OF SECONDARY ENDPOINTS

Secondary endpoints include duration of response and progression-free survival. Duration of response is defined as time from response to disease progression or death. Progression-free survival is defined as the time from study entry until progression or death. Duration of response and progression-free survival will be estimated using the Kaplan-Meier method. Where possible, blood samples and bone marrow samples will be used for additional research studies, which may include functional analyses of immune-cell subsets, analyses for cytokines, chemokines, antibodies, tumor cell antigen targets, and/or other markers. Due to the sample size, the results from those efforts will be exploratory, and the main goal is to generate data for future studies.

Abbreviated Title: Revlimid maintenance for MM

Version Date: 01/06/2017

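### Response assessments follow cycle numbers while PFS runs in calendar time, so delayed cycles tend to postpone detection of progression; the effect is small and cheap to remove

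*Combined protocol and SAP*

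**What the plan says.** Section 6.2.1 states: "Response assessments will be performed on Day 1 (+/- 3 days) of cycles 2, 4 and 7", and then "on Day 1 (+/-3 days) of every third cycle starting at cycle 10 at scheduled clinic visits". Sections 3.3.5.2 and 3.3.5.3 and Study Calendar footnotes f and g put the urine and serum myeloma tests on the same cycle days. No calendar-week schedule is given as an alternative. Section 3.2 fixes the cycle at 28 days.

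Three provisions bear on how far those days can move:
- Footnote m of the Study Calendar, repeated in 3.3.5: "Day 1 may be delayed for up to one week for Cycle 2 and beyond".
- Section 8.1 expects interruptions: "lenalidomide will be held and restarted in accordance with accepted clinical dose modification strategies".
- Section 3.5.1.2 lists among the reasons for removal from therapy: "Toxicity has not resolved after 8 weeks of withholding treatment".

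For low platelets or neutrophils, 3.3.2 and 3.3.3 call for a weekly blood count during a hold; they name no myeloma test. Section 3.3.5.7 adds a general permission: "Additional laboratory studies and clinic visits may be performed as clinically indicated".

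PFS starts at treatment start in 6.2.4 and at study entry in 8.3; both are calendar clocks. Section 8.3 gives the analysis: "Duration of response and progression-free survival will be estimated using the Kaplan-Meier method".

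**The concern.** The endpoint is measured on one clock and looked for on another. When Day 1 slips, the next scheduled myeloma tests slip with it, while PFS time keeps running. Much of progressive disease in 6.2.2.1 is biochemical (serum or urine M-component, free light chains). Follow-up skeletal surveys are optional, and after baseline the marrow is scheduled only at CR or progression. The cycle-timed tests are therefore the main systematic detector.

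If patients who tolerate the drug poorly have more delays, their progression will on average be found later, and the Kaplan-Meier curve will read slightly high for a reason unrelated to disease control. PFS is the first secondary objective in 1.1.2. For duration of response the direction is unclear, because a late assessment can postpone the recorded start of a response as well as its end.

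**Working it through.** **Design figure in the plan.** None is given for PFS. The only computed figure is the power of the primary test in 8.1. A two-sided paired t-test with n = 28, effect 0.67 SD and alpha 0.013 (27 degrees of freedom, noncentrality 0.67 × √28 = 3.55) gives 80.4%, which matches the stated 80%. Assessment timing does not enter it.

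**Calendar with no delay.** Day 1 of cycle k falls at week 4(k − 1). Cycles 2, 4, 7 and 10 are weeks 4, 12, 24 and 36, and the later gap is 3 × 4 = 12 weeks.

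**Gap and mean lag.** If progression is uniform within a gap, mean lag = gap / 2.
- On schedule: 12 weeks, lag 6.
- One one-week slip: 13 weeks, lag 6.5.
- One-week slips in three consecutive cycles: 12 + 3 = 15 weeks, lag 7.5.
- One 8-week hold, assuming that the cycle count stops: 12 + 8 = 20 weeks, lag 10.

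The first three need only footnote m. The last needs an assumption that the protocol does not state. If every cycle slips a week, Day 1 of cycle k falls at week 5(k − 1), so cycle 10 moves from week 36 to week 45 and cycle 25 from week 96 to week 120.

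**Why the average effect is much smaller than the lag in one stretched gap.** Suppose a hold after week 36 moves the visits at weeks 48, 60 and 72 to weeks 56, 68 and 80.
- Progression after the hold starts but before week 48 is dated 8 weeks late.
- Progression in weeks 48 to 56 is found at week 56 instead of 60, which is 4 weeks early.
- Progression in weeks 56 to 60 is found at week 68 instead of 60, which is 8 weeks late.

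Over the 12 weeks from 48 to 60 the mean shift is (8/12)(−4) + (4/12)(8) = 0. The net delay comes from the one disturbed interval.

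**Simulation.** The assumptions are exponential PFS with medians of 13, 31 and 46 months (values taken from Table 1 as a range), 300,000 simulated patients per scenario, and progression dated at the first assessment after it occurs. Hold and delay rates are assumed; the protocol gives none. Where there is a hold, it is one 8-week hold at a random time, with the count stopped.

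| Scenario | Mean shift, all progressors (weeks) | Rise in 52-week PFS (points) |
|---|---|---|
| 25% of patients held | about 0.2 | 0.2 to 0.6 |
| 50% held | 0.4 to 0.5 | 0.5 to 1.0 |
| 100% held | 0.8 to 0.9 | 0.9 to 2.1 |
| Every cycle one week late, every patient | 1.4 to 1.6 | 0.9 to 2.1 |

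A single one-week slip in 25% of patients leaves the 52-week estimate practically unchanged (0.5536 against 0.5528 at the 13-month median).

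The landmark matters. Week 84 coincides with a planned visit, and there the every-cycle scenario adds 2.4 to 4.1 points (0.7481 to 0.7721 at the 46-month median; 0.3577 to 0.3989 at the 13-month median).

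**Sampling error.** With n = 28 and no censoring, the standard error is √[p(1 − p)/28]. For p = 0.53 it is √(0.2491/28) = 0.094; for p = 0.84 it is √(0.1344/28) = 0.069. That is about 7 to 9 points at week 52. At week 84, p = 0.3577 gives √(0.2298/28) = 0.091.

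**The case against.** The strongest reply is that the protocol never says a hold stops the cycle count. Section 3.5.1.2 is a removal criterion and does not mention visits or numbering. The only explicit slip is one week per cycle, so one may equally read that cycles and visits continue through a hold, each at most a week late. This stands: the 20-week gap and 10-week lag are conditional. Supply of drug one cycle at a time (3.2) ties cycles to dosing, but does not settle it.

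A reader might also infer that each interrupted patient's PFS is overstated. The documents do not support that. A moved visit can catch a later progression sooner, as shown above, and symptoms or interim tests can reveal progression between visits. Nor do the 12% to 27% in Table 1 show how often the mechanism operates: they are permanent discontinuations for adverse events in the lenalidomide arms, not holds.

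Finally, the protocol has partial safeguards. Section 3.3.5.7 allows extra tests, 6.1 lets patients have protein markers measured elsewhere between visits, and 6.2.1 requires assessment at progression. These narrow the gap without closing it. The first two are discretionary, the third presupposes that progression has been found, and a silent rise in M-protein may prompt no test. It is also fair that PFS here is a descriptive single-arm estimate with no comparison to bias.

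**Conclusion.** The point holds in a limited form. Assessments are tied only to cycle number, each Day 1 from Cycle 2 may slip, and PFS runs in calendar time, so delays tend on average to postpone detection and lengthen PFS. The size is about 0.2 to 2.1 points on 52-week PFS in the hold and every-cycle scenarios. It is close to nil for isolated one-week slips and somewhat larger at a landmark that coincides with a planned visit. All of this is well within one standard error at 28 patients. It rests on assumed hold and delay rates, exponential PFS and, for the hold scenarios, a stopped cycle count. The primary endpoint, its power and the sample size are unaffected. This is a worthwhile low-cost improvement to a secondary endpoint, not a flaw that threatens the trial.

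**What to change.** In 6.2.1, 3.3.5.2, 3.3.5.3 and footnotes f and g, schedule response assessments and myeloma tests at weeks 4, 12, 24, 36 and every 12 weeks from Cycle 1 Day 1, whether or not lenalidomide is held or a cycle is delayed. State the window. Plus or minus one week would serve: it is wider than the present plus or minus 3 days and lets the tests coincide with a Day 1 visit up to a week late. For a patient on schedule the nominal weeks are those of the present plan.

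State also whether cycle numbering and visits continue during a hold, and reconcile the one-week Day 1 limit with the 8-week withholding criterion. Calendar scheduling makes assessment timing independent of the answer.

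The cost is protocol wording and almost no extra tests. The downside is that a held patient, or one whose delays add up to more than a week, may need blood and urine tests apart from the cycle visit; 6.1 already allows protein markers at an outside institution. The change does not reach patients who have stopped therapy, whose further follow-up remains at the investigator's discretion under footnote l.

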6.2.2.1 Evaluation of Response Criteria

- **Stringent Complete Response (sCR)**

Complete Response as defined below plus:

Normal FLC ratio and absence of clonal cells in bone marrow by immunohistochemistry or immunofluorescence (presence/ absence of clonal cells is based on the kappa/ lambda ratio).

- **Complete Response (CR)**
Negative immunofixation on the serum and urine and disappearance of any soft tissue plasmacytomas and $\leq 5\%$ plasma cells in bone marrow. Patients in whom the only measurable disease is by serum FLC levels: CR in such patients indicates a normal FLC ratio of 0.26 to 1.65 in addition to CR criteria listed above.
- **Very Good Partial Response (VGPR)**
Serum and urine M-protein detectable by immunofixation but not on electrophoresis or 90% or greater reduction in serum M-protein plus urine M-protein level $<100\text{mg}$ per 24h. If the serum and urine M-protein are unmeasurable, a $\geq 90\%$ decrease in the difference between involved and uninvolved FLC levels is required in place of the M-protein criteria.
- **Partial Response (PR)**
 $\geq 50\%$ reduction of serum M-protein and reduction in 24-h urinary M-protein by $\geq 90\%$ or to $<200\text{mg}$ per 24h. If the serum and urine M-protein are unmeasurable, a $\geq 50\%$ decrease in the difference between involved and uninvolved FLC levels is required in place of the M-protein criteria.
- **Minimal Response (MR)**
 $\geq 25\%$ but $\leq 49\%$ reduction of serum M protein and reduction in 24-hour urine M-protein by 50%-89% In addition to the above criteria, if present at baseline, 25%-49% reduction in the size of soft tissue plasmacytomas is also required . If the serum and urine M-protein are unmeasurable, a 25- 49% decrease in the difference between involved and uninvolved FLC levels is required in place of the M-protein criteria. No increase in size or number of lytic bone lesions is required (development of compression fracture does not exclude response)
- **Stable Disease (SD)**
Not meeting criteria for CR, VGPR, PR, MR or progressive disease. All categories also require no known evidence of progressive or new bone lesions if radiographic studies were performed. Radiographic studies are not required to satisfy these response requirements.
- **Progressive disease (PD)**
Requires any one or more of the following:
 - Increase of $\geq 25\%$ from baseline or lowest reponse value in Serum M component, Urine M component, FLC or bone marrow plasma cell percentage. Lowest response value does not need to be a confirmed value.
 - Serum M-component absolute increase must be $\geq 0.5\text{g/dl}$. The serum M-component increases of $\geq 1\text{ gm/dl}$ are sufficient to define relapse if starting M-component is $\geq 5\text{g/dl}$.
 - Urine M-component absolute increase must be $\geq 200\text{mg/24h}$
 - Only in patients without measurable serum and urine M-protein levels: the absolute increase in difference between involved and uninvolved FLC levels must be $>10\text{mg/dl}$.

Abbreviated Title: Revlimid maintenance for MM

Version Date: 01/06/2017

- Only in patients without measurable serum and urine M protein levels and without measurable disease by FLC levels, bone marrow plasma cell absolute percentage must be $\geq 10\%$
- Definite development of new bone lesions or soft tissue plasmacytomas or definite increase in size of existing bone lesions or soft tissue plasmacytomas
- Development of hypercalcemia (corrected serum calcium > 11.5 mg/dL) that can be attributed solely to the plasma cell proliferative disorder
- **Refractory Myeloma**
Refractory myeloma is defined as disease that is nonresponsive while on primary or salvage therapy, or progresses within 30 days of last therapy. Nonresponsive disease is defined as either failure to achieve minimal response or development of progressive disease (PD) while on therapy.
- **Relapse from CR**
Any one or more of the following:
 - CR patients will need to progress to the same level as VGPR and PR patients to be considered PD. A positive immunofixation alone is therefore not sufficient.
 - Development of $\geq 5\%$ plasma cells in the bone marrow
 - Appearance of any other sign of progression (ie, new plasmacytoma, lytic bone lesion, hypercalcemia)

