2.1.2 Exclusion Criteria

- 2.1.2.1 Patients with progressive or refractory MM, as defined by International Myeloma Workshop Consensus Panel criteria provided in section [6.2](#)
- 2.1.2.2 Refractory to lenalidomide in the most recent line of therapy, as defined by the International Myeloma Consensus Panel criteria [47]- as failure to achieve minimal response or development of progressive disease while on lenalidomide or within 30 days of lenalidomide therapy
- 2.1.2.3 Patients who are receiving any other investigational agents with the intent to treat myeloma. Permitted concurrent therapies include:
 - Bisphosphonates
 - Radiotherapy to single stable disease site
- 2.1.2.4 Plasma cell leukemia
- 2.1.2.5 Pregnant or lactating females. Because there is a potential risk for adverse events to nursing infants secondary to treatment of the mother with lenalidomide, lactating females must agree not to breast feed while taking lenalidomide.
- 2.1.2.6 Uncontrolled hypertension or diabetes
- 2.1.2.7 Active hepatitis B or C infection

Abbreviated Title: Revlimid maintenance for MM

Version Date: 01/06/2017

- 2.1.2.8 Diagnosed or treated for another malignancy within 3 years prior to study enrollment, with the exception of complete resection of non-melanoma skin cancer, or an in situ malignancy.
- 2.1.2.9 Previous diagnosis of another malignancy with any evidence of residual disease.
- 2.1.2.10 Patients seropositive for the human immunodeficiency virus (HIV), and/or those who are taking anti-retroviral treatment for HIV/AIDS
- 2.1.2.11 Prior organ transplant requiring immunosuppressive therapy
- 2.1.2.12 Prior allogeneic stem cell transplant
- 2.1.2.13 Patients requiring continuous, systemic immunosuppressive therapy
- 2.1.2.14 Patients with myocardial infarction within 6 months prior to enrollment, New York Heart Association (NYHA) Class III or IV heart failure, uncontrolled angina, severe uncontrolled cardiac arrhythmias, or electrocardiographic evidence of acute ischemia
- 2.1.2.15 Patients with conditions that would prevent absorption of the study drug
- 2.1.2.16 Uncontrolled intercurrent illness including but not limited to uncontrolled infection or psychiatric illness/social situations that would compromise compliance with study requirements
- 2.1.2.17 Significant neuropathy \geq Grade 3 at baseline
- 2.1.2.18 Contraindication to concomitant anticoagulation prophylaxis
- 2.1.2.19 Major surgery within 1 month prior to enrollment

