6.2.3 Duration of Best Response

The duration of overall response is measured from the time measurement criteria are met for best response until the first date that recurrent or progressive disease is objectively documented.

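### Minimal response is written as closed bands with stable disease as the remainder, so some patients who exceed a band are graded below weaker responders and could be treated as lenalidomide-refractory at screening

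*Combined protocol and SAP*

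**What the plan says.** Section 6.2.2.1 sets out the response ladder.

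- **MR** needs a serum fall of at least 25% and at most 49%, joined by 'and' to a urine range: "reduction of serum M protein and reduction in 24-hour urine M-protein by 50%-89" per cent. If a soft tissue plasmacytoma was present at baseline, "25%-49% reduction in the size of soft tissue plasmacytomas is also required". When serum and urine are both unmeasurable, the substitute is "a 25- 49% decrease in the difference between involved and uninvolved FLC levels". MR adds a bone condition: "No increase in size or number of lytic bone lesions is required".
- **PR** has no upper limit. It asks for at least a 50% "reduction of serum M-protein and reduction in 24-h urinary M-protein by" at least 90%, or to below 200 mg per 24 h. Neither PR nor VGPR mentions plasmacytomas; CR does, requiring that they disappear.
- **SD** is the remainder: "Not meeting criteria for CR, VGPR, PR, MR or progressive disease".

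The categories are used at screening. Section 2.2.1 has the response to prior treatment documented by the 6.2 criteria. Exclusion 2.1.2.2 defines lenalidomide-refractory disease, in the most recent line, as "failure to achieve minimal response or development of progressive disease while on lenalidomide" or within 30 days of it. The refractory definition in 6.2.2.1 applies the same test to any therapy, and exclusion 2.1.2.1 points to it. Inclusion 2.1.1.1 admits stable disease or better.

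On study, 6.2.6 counts PR, VGPR and CR as overall response. Section 6.2.3 has duration "measured from the time measurement criteria are met for best response", and 8.3 starts it at response.

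**The concern.** A response ladder should never grade a patient lower for doing better on one component. Because MR is closed at the top and SD collects every unmatched case, a patient can leave MR by improving, yet fall short of PR on the other component, and so be graded SD.

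The MR/SD line is also an eligibility line. If lenalidomide was part of the most recent treatment, a responder graded SD for this reason has, on the literal text, failed to achieve MR and meets 2.1.2.2. Two investigators could reach opposite eligibility decisions on the same laboratory values.

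Separately, a plasmacytoma condition that appears at MR but not at PR or VGPR lets a patient be called PR whose plasmacytoma response would not have allowed MR.

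**Working it through.** The plan gives no figure on this point, so the check is to apply the 6.2.2.1 rules literally: PR first, then MR, otherwise SD.

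**Assumptions.** Baseline urine M-protein is 2,000 mg/24 h unless noted (not from the documents). M-protein is still visible on electrophoresis, so VGPR is not met by that route. There is no progression and there are no new bone lesions. Residual urine = baseline × (1 − fall).

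| Serum fall | Urine fall | Residual urine (mg/24 h) | Plasmacytoma | Why | Grade |
|---|---|---|---|---|---|
| 40% | 70% | 600 | none | both bands met | MR |
| 60% | 70% | 600 | none | serum above 49%; urine below 90% and not under 200 mg | SD |
| 80% | 85% | 300 | none | same | SD |
| 40% | 95% | 100 | none | urine above 89%; serum below 50% | SD |
| 30% | 60% | 800 | shrinks 60% | plasmacytoma above 49% | SD |
| 49.5% | 60% | 800 | none | between 49% and 50% | SD |
| 40% | 89.5% | 210 | none | between 89% and 90% | SD |
| 40% | no urine M-protein | 0 | none | no 50% to 89% urine fall possible | SD |
| 55% | no urine M-protein | 0 | none | urine below 200 mg accepted | PR |
| 40% | 70% | 600 | unchanged | MR plasmacytoma condition fails | SD |
| 50% | 90% | 200 | unchanged | PR has no plasmacytoma condition | PR |

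Rows 2 to 4 do at least as well as row 1 on both components and are graded lower.

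**Extent of the unmatched region.** Take serum falls of 25% to 100% (76 values) and urine falls of 50% to 100% (51 values) in 1% steps, with no plasmacytoma: 76 × 51 = 3,876 combinations, all at or above both lower MR limits. MR covers 25 × 40 = 1,000.

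- Baseline urine 2,000 mg/24 h: PR or better needs serum ≥50% (51 values) and urine ≥90% (11 values), so 51 × 11 = 561. SD gets 51 × 40 + 25 × 11 = 2,040 + 275 = 2,315, or 59.7%.
- Baseline urine 500 mg/24 h: residual below 200 mg needs a fall above 60% (40 values), so PR or better covers 51 × 40 = 2,040. SD gets 51 × 11 + 275 = 561 + 275 = 836, or 21.6%.

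These are shares of combinations, not of patients. With MR as a pair of lower thresholds, both counts become 0, since every combination meets the thresholds by construction.

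**What is not a problem.** The free light chain band has a single component and PR starts at 50%, so only the sliver between 49% and 50% is unmatched. The lytic-lesion condition is largely shared, because the SD paragraph requires no known progressive or new bone lesions in every category. Patients who fully meet PR or VGPR are not downgraded.

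**Eligibility chain.** Section 2.2.1 grades by 6.2; rows 2 to 8 come out SD; 2.1.2.2 makes not reaching MR on lenalidomide sufficient for exclusion. In addition, 2.1.1.1 admits SD, while 2.1.2.1, through the 6.2.2.1 refractory definition, excludes disease that did not reach MR on therapy, whatever the drug. Those passages conflict even for patients correctly graded SD.

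**The case against.** **The criteria are an adopted consensus standard.** They are presented as such and the source was not available here. This stands to the extent that the transcription should be checked before anything is reworded. It does not remove the problem, because 2.2.1 sends graders to the protocol's own text.

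**Any sensible investigator reads the bands as floors and minimal response as at least minimal.** Many may. But the upper limits are explicit, nothing in the protocol says that exceeding one still counts as MR, and the residual wording of SD supplies the opposite answer.

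**Serum-only disease.** A reader might infer that every MR is lost in patients without urine M-protein. That reads MR strictly and PR generously: PR also words its urine condition as a reduction. Section 6.2.1 treats disease as measurable by serum or urine, and asks for urine confirmation only when urine is the primary determinant. A sensible reading is therefore available. What stands is that MR does not state it and lacks PR's 200 mg alternative.

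**Duration of response.** A reader might infer that start dates will be wrong because of the MR bands. The documents do not support this. Section 8.3 does not say which categories count as response, and 6.2.6 counts only PR or better. MR-versus-SD errors move a start date only if MR counts as response, which is nowhere stated.

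**SD is itself eligible, and 2.1.2.2 covers only lenalidomide in the most recent line.** This is true, and it limits the harm from 2.1.2.2 to that group. The wider clash between 2.1.1.1 and 2.1.2.1 remains.

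**Conclusion.** The point holds as a defect of wording. Read as written, MR is not an ordered step between SD and PR: some patients who exceed one band without meeting PR are graded below weaker responders, and serum-only disease has no stated route to MR. The main consequence is at screening, where a misgraded responder whose most recent line included lenalidomide could be treated as refractory. The plasmacytoma gap is a second consequence: it can affect who is counted as PR, and through that the overall response rate and duration of response.

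The primary endpoint (cell counts in 8.1) and its power do not use response categories. PFS is unaffected, since progression is judged from measured values and not from MR. The overall response rate does not count MR, so MR-versus-SD errors leave it unchanged.

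A reader might try to put a number on it, for example 5% to 15% of 28 patients (0.05 × 28 = 1.4 to 0.15 × 28 = 4.2). The documents give no response distribution to support such a share, and candidates excluded at screening are not among the 28 enrolled. The number affected cannot be derived from the documents.

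**What to change.** After checking the transcription against the cited consensus criteria, amend 6.2.2.1 so that:

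- MR is assigned when its lower thresholds are met and PR is not, with no upper limits;
- the serum and urine components each apply only if measurable at baseline, so that neither serum-only nor urine-only disease is shut out;
- MR carries PR's alternative of urine below 200 mg per 24 h. Without it, urine going from 250 to 180 mg (70/250 = 28% fall) with serum down 40% stays SD, while the same urine with serum down 50% is PR;
- the plasmacytoma condition is stated consistently, in 'at least' form, at MR, PR and VGPR.

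Write 'MR or better' where the refractory definition (6.2.2.1) and exclusion 2.1.2.2 refer to minimal response. Separately, the sponsor must reconcile 2.1.1.1, which admits stable disease, with 2.1.2.1 and the refractory definition, under which not reaching MR is refractory.

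The cost is a wording amendment, with no new tests, visits or patients. Responses already graded under the present text, including those at screening, would need a check against the amended rules.
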